#### 8.4.1.2 Anemia Response

Anemia response rate is defined as the proportion of subjects who achieved anemia response.

Baseline hemoglobin mentioned below is defined in Section 7.2.2. The transfusion dependency status (transfusion independent and transfusion dependent) mentioned below

are based on investigators reporting in the Study Cancer History Form according PRBC transfusion events ( $\geq 6$  units within 12 weeks and  $\geq 1$  unit within 28 days) prior to the start of study treatment.

For a subject who is transfusion independent (TI) at baseline with hemoglobin value < 10 g/dL, the subject will be considered as achieving anemia response if the post baseline hemoglobin level increases by  $\ge 2 \text{ g/dL}$  from baseline without receiving PRBC transfusion (for any reason) within 2 weeks and without any erythropoietin, erythropoietin mimetics within the last 4 weeks prior to the increase in hemoglobin level by  $\ge 2 \text{g/dL}$  was observed. Hemoglobin values after 30 days post last date of study treatment, the start of post-study treatment or disease progression whichever is earlier will not be considered in the analysis of anemia response.

For a subject who is transfusion dependent (TD) at baseline, anemia response is defined as a period of at least 12 consecutive weeks without PRBC transfusion after the first dose of study drug and on or prior to 30 days post last dose of study drug, the start of post-study treatment, disease progression or death, whichever occurs earlier.

[figure not shown]
Subjects who are baseline transfusion independent with baseline hemoglobin of  $\geq 10$  g/dL will not be included in the analysis since these subjects are not evaluable for anemia response.

Anemia response rate will also be summarized for all subjects who are evaluable for anemia response in the Full Analysis Set and by transfusion dependency status at baseline.

Missing post-baseline anemia response in Full Analysis Set applicable to evaluation of anemia response are considered as non-responders of anemia response.

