#### 8.5.1.6 Post Baseline Red Blood Cell Transfusion

Post Baseline Red Blood Cell transfusion (for any reason) evaluation period is from after the first dose of study drug to earliest day of on or before the last dose of study drug + 30 days, or the start of post-study treatment.

Post baseline transfusion independent rate will be calculated as the proportion of subjects who achieved PRBC transfusion independent during the treatment period. PRBC Transfusion independent is defined as a period of at least 12 weeks (≥ 84 days) with no PRBC transfusions during the evaluation period. In addition, the rate of conversion will be calculated as proportion of subjects being post-baseline PRBC transfusion independent from baseline PRBC transfusion dependent.

The duration of PRBC transfusion independent will also be summarized for overall and by transfusion status at baseline (transfusion dependent and transfusion independent). The duration of transfusion independence is defined as the first time period that a subject received no PRBC transfusions for at least 12 weeks ( $\geq$  84 days). The descriptive

statistics (median and range) will be provided for the duration of transfusion independence.

Incidence rate of PRBC transfusion/subject/month, defined as total number of PRBC transfusion from all subjects divided by total duration of treatment from all subjects (months).

Time from first date of study treatment to the first time receiving 2 or more units of PRBC transfusion will be summarized.

Above endpoints will be analyzed in the Full Analysis Set.

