#### 8.5.1.7 Duration of Anemia Response

Duration of anemia response will be summarized by baseline transfusion status.

For subjects who were transfusion independent at baseline and achieved anemia response, the evaluation period for duration of anemia response is from achieving anemia response to 30 days after last dose of study treatment. Duration of anemia response is defined as number of days from the first date of achieving anemia response described in Table 6 to the date of loss anemia response as described in Table 7.

Table 6. Date of First Anemia Response for Duration of Anemia Response

Transfusion Status at baseline	Date of First Response
TI	On the first date observing hemoglobin level increase by $\geq 2$ g/dL from baseline without receiving PRBC transfusion within the last 2 weeks or any erythropoietin, erythropoietin mimetics within 4 weeks prior to the increased hemoglobin level
TD	On the first date observing no PRBC transfusion for at least 12 weeks

Table 7. Event and Censoring Condition for Duration of Anemia Response

[figure not shown]
Transfusion Status at baseline	Event/Censor	Date of Event/Censor
TI	Event: 1) decrease in hemoglobin level by 2 g/dL or more from the hemoglobin level at the first occurrence of achieving anemia response, or 2) need for PRBC transfusion before disease progression for the bleeding event* which was unrelated to navitoclax/ruxolitinib or 3) use of any erythropoietin, erythropoietin mimetics within 30 days of last dose of study drug	Earliest date of events
	Censor: if no above-mentioned events observed within 30 days of last dose of study drug	The last date of hemoglobin assessment after achieving anemia response, 30 days post last dose of study treatment, start of post-study treatment, disease progression, or death, whichever is earlier.  Date of achieving anemia response will be the censor date if no hemoglobin assessment is obtained after achieving anemia response.

\* Bleeding event is defined as a treatment emergent hemorrhage event from narrow search of Standardized MedDRA Queries (SMQ). PRBC occurring between the start of bleeding event and end/ongoing will be considered as need for PRBC transfusion for bleeding.

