For subjects who were transfusion dependent at baseline, the duration of anemia response is defined as the 1st time period that a subject received no PRBC transfusions for at least 12 weeks ( $\geq$  84 days). The descriptive statistics (median and range) will be provided for the duration of anemia response.

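### Duration of anemia response (SAP 8.5.1.7): the transfusion event in Table 7 is worded too narrowly, relapse for loss of the response can be censored, and transfusion-dependent responders have no event or censoring rule

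*SAP*

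**What the plan says.** Duration of anemia response is an exploratory endpoint (SAP 3.3), reported by baseline transfusion status.

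**Transfusion independent (TI) at baseline.** SAP 8.5.1.7, Table 7, lists three loss events: a hemoglobin fall of at least 2 g/dL from the level at first response; "need for PRBC transfusion before disease progression for the bleeding event* which was unrelated to navitoclax/ruxolitinib"; and use of erythropoietin or a mimetic. The footnote defines a bleeding event and when a transfusion belongs to one. It says nothing about transfusion for anemia. The censoring row begins "Censor: if no above-mentioned events observed within 30 days of last dose of study drug", and disease progression is one of the possible censoring dates.

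**Transfusion dependent (TD) at baseline.** Table 7 as read shows no TD row. The paragraph after it defines duration as the first PRBC-free period of at least 84 days and adds: "The descriptive statistics (median and range) will be provided for the duration of anemia response". Table 6 dates the start of a TD response as "On the first date observing no PRBC transfusion for at least 12 weeks".

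**Duration of transfusion independence.** SAP 8.5.1.6 uses the same construction: "The duration of transfusion independence is defined as the first time period that a subject received no PRBC transfusions for at least 12 weeks". Its evaluation period ends at the "earliest day of on or before the last dose of study drug + 30 days, or the start of post-study treatment".

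**Related rules.**
- SAP 8.1 defines disease progression as relapse or progressive disease, excludes data after cutoff, and prescribes Kaplan-Meier for all time-to-event endpoints.
- SAP 8.2 says the censoring rules are in the sub-sections.
- SAP 8.5.2 sends exploratory endpoints back to 8.1.
- Table B-4 makes loss of anemia response lasting at least 1 month a relapse criterion.

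**The concern.** An anemia-response duration should end when the patient again needs blood for anemia. As worded, event 2 counts a transfusion for an unrelated bleed and leaves out one for recurrent anemia. An investigator-recorded loss of this same response can also become a censoring date, and that censoring is informative. Both tend to lengthen the reported TI duration.

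For TD responders, and for duration of transfusion independence, a period still running at cutoff would be entered at its length so far, which shortens the reported duration. The two strata could therefore err in opposite directions, and comparing them could mislead. Duration of disease response, including anemia, is a stated exploratory objective.

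**Working it through.** The documents give no expected duration, event count or precision for this endpoint, so there is no stated figure to reproduce. The check sets the rules side by side and then illustrates size under assumed inputs.

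**1. Event 2.** Hypothetical subject: baseline hemoglobin 8.0 g/dL, response at 10.0, later transfused for anemia at 8.5. The gain over baseline is 8.5 − 8.0 = 0.5, so the 2 g/dL gain is gone. The fall from response is 10.0 − 8.5 = 1.5, below 2, so event 1 does not fire. Event 2 does not fire because there was no bleed. The response continues, and the transfusion may itself raise the hemoglobin on which event 1 depends. By contrast, SAP 8.4.1.2 lets a TI subject attain response only "without receiving PRBC transfusion (for any reason) within 2 weeks", and 8.5.1.6 also evaluates transfusions given for any reason.

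**2. Relapse.** Progression includes relapse (8.1), and relapse includes loss of anemia response (Table B-4). Table 7 lists progression only as a censoring date, while duration of SVR35 (8.5.1.2) counts relapse as an event. If the same hypothetical subject fell to 8.1 g/dL, the drop would be 1.9, so there would be no event 1. A relapse recorded then would be censored.

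**3. TI size.** Assume exponential loss with a true median of 40 weeks. A share p of losses is uncounted, the subject stays at risk, and event 1 follows d weeks later. The Kaplan-Meier median is then 40 + (40/ln 2) × ln(1 − p + p × 2^(d/40)). If event 1 never follows, it is 40 × ln(1/(1 − 0.5/(1 − p)))/ln 2.

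| p | d = 0 | 4 | 12 | 26 | never |
|---|---|---|---|---|---|
| 10% | 40.0 | 40.4 | 41.3 | 43.2 | 46.8 |
| 25% | 40.0 | 41.0 | 43.2 | 47.7 | 63.4 |

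The column d = 0 is the case in which the hemoglobin event coincides with the transfusion; the bias is then nil. Simulation agrees to within about 0.2 week.

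**4. TD size, independent censoring.** Assume duration T = 12 weeks plus an exponential residual, and follow-up uniform on (a, b). If open periods enter as complete, the raw median m solves P(T > m) × P(follow-up > m) = 0.5. For a true median of 40 weeks and follow-up U(24,72): 2^(−(32.4 − 12)/28) × (72 − 32.4)/48 = 0.60 × 0.825 ≈ 0.50, so m ≈ 32.4, which is 19% too low.

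| Follow-up (weeks) | True 40 | True 60 | True 100 |
|---|---|---|---|
| U(12,96) | 30.2 (−24%) | 36.4 (−39%) | 42.6 (−57%) |
| U(12,196) | 34.7 (−13%) | 46.0 (−23%) | 60.9 (−39%) |
| U(48,144) | 40.0 (0%) | 54.9 (−9%) | 68.9 (−31%) |
| U(96,196) | 40.0 (0%) | 60.1 (0%) | 97.7 (−2%) |
| U(24,72) | 32.4 (−19%) | 37.4 (−38%) | 41.7 (−58%) |

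U(24,72) represents an analysis at the Week 24 trigger in SAP 11.0 with an assumed 48-week enrollment span. Kaplan-Meier returns the true median in every cell except true 100 under U(12,96) and U(24,72), where it is not reached.

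**5. TD size, informative censoring.** This uses a Gaussian copula between duration and follow-up, for the first four follow-up patterns. At correlation 0.3, Kaplan-Meier is 0% to 13% too high where reached and the raw median 0% to 55% too low. At 0.6 the two err about equally in five cells (Kaplan-Meier / raw):
- U(12,96): true 40, +12% / −13%; true 60, +33% / −29%.
- U(12,196): true 40, +4% / −4%; true 60, +10% / −11%; true 100, +26% / −26%.

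These are all the cells with follow-up starting at 12 weeks in which the Kaplan-Meier median is reached.

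**The case against.** - **Event 2 may be a drafting slip.** Probably so. A programmer following the text would still code the wrong events, so it needs correcting. A reader might infer that Table 7 contradicts the response definition in 8.4.1.2. It does not: that rule governs attaining response, to keep a transfusion effect from passing as a hemoglobin rise, and does not define loss. The two are out of line, not contradictory.
- **Not every relapse is lost.** This stands. A relapse that also meets a listed event still counts, and under protocol 5.4.1 treatment can continue after progression.
- **The TD limb rests partly on silence.** SAP 8.1 and 8.5.2 could be read as requiring Kaplan-Meier, and SAP 1.0 leaves programming detail to a separate plan. A reader might infer that the SAP definitely treats open periods as complete; it never says so. But 8.2 places censoring rules in the sub-sections, none is given here, and median and range are specified. The texts need reconciling.
- **An on-treatment description is legitimate.** This stands in part. The first PRBC-free period within the limits of 8.5.1.6 can be a target in its own right, and a period ended by those limits is then complete. Only truncation at data cutoff clearly leaves it incomplete.
- **Size is assumed, and Kaplan-Meier is not error-free.** Both stand. Cohort 1a was fully enrolled by 10 April 2019, 1,392 days or about 199 weeks before SAP version 4.0 (31 January 2023), so the short-follow-up case does not fit it unless early discontinuation shortens follow-up.

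**Conclusion.** The point holds in three parts.

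1. As written, event 2 leaves out the transfusions that matter most for an anemia endpoint. Confidence is high.
2. Relapse recorded for loss of anemia response is censored when no listed event is observed, which is inconsistent with duration of SVR35.
3. TD duration and duration of transfusion independence lack an event and censoring rule. Periods open at cutoff would enter as complete and understate duration. For periods ended by last dose + 30 days or post-study treatment, understatement depends on whether an on-treatment description is the target. Confidence is moderate.

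Confidence in size is low. The ranges (TI 40 to 47 weeks at 10% uncounted losses and 40 to 63 at 25%, against a true 40; TD 0% to 58% too low under independent censoring) rest wholly on assumed medians, follow-up and shares of missed losses. The documents give none of these.

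A reader might infer that the study's main efficacy results are affected. They are not: the primary endpoint and the anemia response rate use other rules, and the endpoints here are exploratory and estimated without formal testing.

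**What to change.** 1. **Table 7, event 2.** Replace with: any PRBC transfusion after achieving anemia response. If an exemption was meant: any PRBC transfusion except for a bleeding event unrelated to navitoclax/ruxolitinib.
2. **Relapse.** Count relapse recorded for loss of anemia response as an event, in TI and TD subjects alike. If the Disease Response Assessment Form does not record the reason, add one sensitivity analysis counting progression, relapse and death as loss. It would also probe informative censoring.
3. **TD row.** Event: first PRBC transfusion after the qualifying period of at least 84 days. Censor open periods at data cutoff or the stated limits, which for TD response in 8.4.1.2 are "on or prior to 30 days post last dose of study drug, the start of post-study treatment, disease progression or death, whichever occurs earlier", with relapse handled as in item 2. For 8.5.1.6, use its own limits or cutoff.
4. **Method.** Use Kaplan-Meier for both strata and for duration of transfusion independence, and report the number of open periods. If an on-treatment description is wanted, say so and label it.
5. **Table 6.** State whether the TD date is the first or last day of the 12 weeks, and use the same start for the TD duration.

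The cost is SAP wording and a small programming change. Transfusions, hemoglobin and bleeding events are already collected. Whether the relapse reason is recorded cannot be seen from the documents.

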# 8.5.1.8 Overall Response Rate (ORR)

ORR is defined as the proportion of subjects who achieve best response of complete remission (CR) or partial remission (PR) per IWG criteria. Subjects who do not have any disease assessment or who have started - post-study treatment prior to achieving best response of CR or PR will be considered as non-responders. Responses achieved after

relapse or progressive disease or starting post-study treatment will not be included. This endpoint will be analyzed in the Full Analysis Set.

# 8.5.1.9 Progression-Free Survival (PFS)

PFS is defined as time from the first date of study treatment to the date of first documented disease progression/relapse per IWG criteria as determined by the investigator, or death due to any cause, whichever is earlier. Disease progression and death after start of post-study treatment are not considered as an PFS event.

For subjects who do not experience a PFS event (disease progression, relapse, or death due to any cause) on or prior to the start of post-study treatment, PFS will be censored at the last adequate disease assessment (where IWG response evaluation is not missing) on or prior to the start of post-study treatment.

[figure not shown]
For subjects without any post baseline disease assessments who did not die, PFS will be censored at Day 1.

PFS will be analyzed in the Full Analysis Set.

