During treatment, all assessments must be performed on the day of the specified visit unless a time window is specified in the schedule of assessments (Appendix C). Refer to Section 3.6 for study visit modifications.

Subjects will continue their treatment until end of clinical benefit, unacceptable toxicity or subject meets other protocol criteria for discontinuation (whichever occurs first). All subjects will have a TCV performed when treatment is discontinued.

Response and progression will be assessed by the Investigator based on the modified International Working Group-Myeloproliferative Neoplasms Research and European Leukemia Net (IWG-MRT/ELN) and as noted in Appendix E.²⁴ Spleen volume will be assessed by an independent central review and interpretations will be transmitted to investigators, as available, and will be utilized in determining response and progression. The evaluation of fibrosis grading and reticulin staining grading may be assessed independently by a central pathologist. Independent interpretations of bone marrow samples are not planned to be transmitted to investigators. Details regarding the determination of clinical response and disease progression are provided in Appendix E.

Follow-Up

Safety Follow-Up: All subjects will have one Safety Follow-up visit approximately 30 days following TCV.

Post-Treatment Follow-Up: For subjects who discontinue study treatment for reasons other than disease progression, a Post-Treatment Follow-up visit will be performed approximately 12 weeks following TCV, then every 12 weeks thereafter to assess disease

status until criteria are met for discontinuation from study (e.g., disease progression, initiation of post-treatment cancer therapy, or subject refusal of post-treatment follow-up visits).

Once disease progression is confirmed or the subject begins a post-study treatment for MF other than the continuation of ruxolitinib (Cohorts 1a, 1b or 3), the subject will enter the Survival Follow-up phase.

Survival Follow-Up: Survival Follow-up will then be performed approximately every 6 months for up to 5 years after TCV (provided informed consent has not been withdrawn for collection of such information). Survival information (e.g., date and cause of death, details of post-treatment cancer therapies including response and progression) may be collected via telephone calls (e.g., to subject or family member), clinic visits, and/or public database searches.

5.2 **Selection of Study Population**

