For study visits with bone marrow sampling, chemistry and hematology labs should be performed on the same day the bone marrow sample is obtained.

Imaging for Spleen Volume Assessment

Assessment of spleen volume must be performed at Screening with an MRI or a CT scan and as outlined in Appendix C. The scans will be transmitted to the central imaging vendor for an independent central review.

The imaging should be acquired as close as possible to the start of study treatment and must be during the Screening period. Image receipt and verification should be received from the central imaging vendor before the subject can be treated. In the event that the baseline image is determined by the independent reviewer to have been performed incorrectly, the baseline MRI/CT should be rescheduled for the earliest date possible prior to dosing. If imaging is utilized to verify subject eligibility, the baseline spleen volume measurement must be requested and the MRI/CT transmitted at least 7 days prior to planned Day 1 dosing to allow adequate time for delivery of results from the central imaging vendor.

After Week 96, an MRI/CT needs to only be performed if disease progression is suspected.

A non-contrast MRI of the abdomen is the preferred imaging modality. A non-contrast CT scan may be performed if MRI is medically contraindicated due to metallic implants (e.g., pacemaker, prosthetic valves). Subjects should have the same imaging modality performed throughout the study for consistency and direct comparison unless a subject

develops a contraindication to MRI during the course of the study, then a change to CT is permitted. All MRI/CT scans performed during the study must be sent to the central imaging vendor for an independent central review.

Physical Examination

Complete or symptom-directed physical examinations (PE) will be performed at the study visits outlined in Appendix C.

A complete physical examination should include the evaluation of the head, eyes, ears, nose, and throat (HEENT); and the following systems: cardiovascular, respiratory, gastrointestinal, musculoskeletal, neurological and dermatological.

A symptom directed physical examination may be limited to those systems associated with symptoms.

All physical examinations should include skin examination, spleen and liver measurement by palpation.

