For disease response assessments performed at Week 36 and 72, a repeat bone marrow biopsy is not required unless disease progression is suspected. The prior bone marrow assessment may be used for the purposes of assessing disease response.

Assessment of disease response is not required after Week 96 unless disease progression is suspected.

5.3.1.2 **Meals and Dietary Requirements**

The absorption of ruxolitinib is not affected by food and ruxolitinib may be taken with or without food.

Food increases the bioavailability of navitoclax independent of meal type (low-fat versus high-fat). Therefore, navitoclax should be taken within 30 minutes of food intake.

Cohort 1b Drug-Drug Interaction (DDI) sub-study subjects only: Subjects may not consume grapefruit or grapefruit products, Seville oranges (including marmalade containing Seville oranges) or Star fruit within the 3-day period prior to the first study drug administration and until the last day of treatment is completed due to possible CYP3A mediated metabolic interaction.

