- For visits with bone marrow sampling, hematology and chemistry labs should be performed on the same day as the bone marrow assessment. Bone marrow biopsy and aspirate as well as cytogenetics will be performed at Screening (results from historical bone marrow samples will not be accepted), Weeks 12 (D85), 24 (D169), 48 (D337) and 96 (D673). All bone marrow sampling must be completed within the ± 7 day window for the study visit. Additional bone marrow sampling and cytogenetics should be performed if disease progression is suspected, at the discretion of the investigator.
- Procedure should be performed if the subject discontinues from the study for a reason other than documented disease progression and if this procedure has not been done within the last 12 weeks.
- MRI (CT allowed if MRI is medically contraindicated), Bone Marrow sampling and Disease Response Assessments to be performed during Post-Treatment FU visits as necessary if disease progression is suspected.
- May be obtained from bone marrow or peripheral blood sampling.
- Bone marrow biopsy/aspirate samples for exploratory biomarker analysis should be split from the samples collected for local clinical assessment. All bone marrow sampling must be completed within the \pm 7 day window for the study visit.
- See Table 7 and Appendix D for the schedule of Pharmacokinetic Assessments for Navitoclax and Ruxolitinib.
- Cohort 1b-DDI only. See Appendix D Table 8.
- Cohort 1b-DDI only for Days 7 and 8. See Appendix D Table 8.
- MRI/CT of the abdomen to determine spleen volume will be conducted at Screening, Weeks 12 (D85), 24 (D169), 36 (D253), 48 (D337), 72 (D505) and 96 (D673). Additional MRI/CT should be performed if disease progression is suspected, at the discretion of the investigator. All MRI/CT assessments must be completed within the \pm 7 day window for the study visit. All MRI/CT must be sent to a central imaging vendor.

obbyje Navitoclax (ABT-263) M16-109 Protocol Amendment 11

EudraCT 2017-001398-17

Table 6. Study Procedures - Navitoclax Alone or in Combination with Ruxolitinib (Continued)

- ff. Disease Response Assessment to be performed at Weeks 12 (D85), 24 (D169), 36 (D253) 48 (D337), 72 (D505) and 96 (D673). For disease assessments performed at Week 36 and 72, a repeat bone marrow biopsy is not required unless disease progression is suspected. The prior bone marrow assessment may be used for the purposes of assessing disease response per modified IWG criteria.

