## 6.4 Dose intensity (DI) and Relative Dose Intensity (RDI)

An observed dose intensity (ODI) will be derived for each subject who receives the study drug based on how it was actually administered. A planned dose intensity (PDI) will also be derived based on the protocol-specified schedule of the study drug.

For ODI it is calculated as:

[figure not shown]
ODI = 
$$\frac{\text{Actual total dose}}{\text{Actual total duration of treatment exposure (days)}}$$

For PDI it is calculated as:

PDI 
$$=$$
  $\frac{\text{Planned total dose over protocol specified}}{\text{Actual total duration of treatment exposure (days)}}$ 

RDI is defined as: RDI =  $(ODI/PDI) \times 100\%$ .

The RDI will be summarized based on the study drug administration form in EDC. Ruxolitinib administered before the first dose of navitoclax is considered as prior study treatment therapy collected in the Study Cancer Prior Systemic Therapies (Myelofibrosis)

form in EDC for Cohort 1 (Cohorts 1a and 1b). Ruxolitinib administered after the last dose of navitoclax for Cohort 1 (Cohorts 1a and 1b) is considered as post-study treatment collected in Post Study Drug Systemic Therapies form in EDC.

The actual total duration of treatment exposure in the above equations is defined as the last dose date minus first dose date + 1 for navitoclax or ruxolitinib, respectively. Descriptive statistics will be presented for navitoclax (for all Cohorts) and ruxolitinib (for Cohort 3, Cohort 1a and Cohort 1b) respectively.

Number and percentage of subjects who have dose reductions or interruptions, will be summarized.

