#### 8.5.1.2 Duration of SVR35

Only subjects who achieved SVR35 will be included in this analysis for duration of SVR35. The Duration of SVR35 is defined as the number of days from the first date of SVR35 achievement to the first date of 1) SVR< 35% AND observing  $\geq$  25% spleen volume increase from nadir (the lowest spleen volume in the previous assessments) or 2) disease progression (relapse or progressive disease) per investigator by IWG/MRT criteria, whichever is earlier. Subjects without the defined event mentioned above will be censored at the last date of the following assessments on or before post-study treatment: MRI/CT scan for spleen volume assessment, bone marrow assessment, lab assessment, disease response assessment.

[figure not shown]

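### PFS censors event-free subjects at their last IWG assessment, but none is required on treatment after Week 96, so the later Kaplan-Meier curve and any median there are biased downward unless clean assessments continue

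*SAP*

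**What the plan says.** - **Censoring.** SAP 8.5.1.9 counts investigator-assessed progression or relapse, or death, at its own date if it precedes post-study treatment. It sets no limit on the gap since the last assessment. Without an event, "PFS will be censored at the last adequate disease assessment (where IWG response evaluation is not missing".
- **Schedule.** Protocol Appendix C, Table 6, note ff: "Disease Response Assessment to be performed at Weeks 12 (D85), 24 (D169), 36 (D253) 48 (D337), 72 (D505) and 96 (D673". Protocol 5.3.1.1, Disease Response Assessment: "Assessment of disease response is not required after Week 96 unless disease progression is suspected". The imaging paragraph there agrees: "After Week 96, an MRI/CT needs to only be performed if disease progression is suspected".
- **Treatment** has no fixed end (Protocol 5.1).
- **Possible later clean assessments.** Table 6 marks a disease response assessment at the treatment completion visit (TCV). The Protocol Synopsis also asks for one whenever imaging or marrow sampling is done.
- **Reporting.** SAP 8.1 plans a Kaplan-Meier curve and, if reached, a median with 95% CI. The SAP has no truncation at Week 96 and no PFS sensitivity analysis.
- **Comparison.** For duration of SVR35, SAP 8.5.1.2 censors at the latest of a wider set: "MRI/CT scan for spleen volume assessment, bone marrow assessment, lab assessment, disease response assessment".

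**The concern.** Kaplan-Meier estimation needs censoring that is unrelated to the coming outcome. After Week 96 a subject still on treatment adds PFS time mainly by having an event or being suspected of one. A subject who stays well is moved back to the Week 96 assessment, although follow-up continued. Whether someone is in the risk set after Week 96 then depends on what happens to them later. If nobody has a clean assessment after Week 96, everyone left in the risk set has an event, and the curve must reach 0 at the last one whatever the true PFS.

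At stake are the late part of the PFS curve and the median, if it falls there. Follow-up can reach that far: Cohort 1a was fully enrolled by 10 April 2019, and the SAP is dated 31 January 2023.

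**Working it through.** The documents give no PFS median, event count, discontinuation rate or data cutoff, so there is no PFS figure to reproduce.

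**Step 1: worked example with assumed counts and no assumed distribution.** Of 34 subjects, 20 are event-free on treatment at Week 96. Six later have an event; 14 stay event-free with no later IWG assessment.

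- At Week 96: 20/34 = 0.588.
- SAP rule, risk set of 6: 0.588 × 5/6 = 0.490 at the first later event, then 0.392, 0.294, 0.196, 0.098, 0.
- All 20 kept at risk: 0.588 × 19/20 = 0.559 at the first later event, and 14/34 = 0.412 at the sixth.

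**Step 2: simulation inputs.**

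- From the documents: IWG assessments at Weeks 12, 24, 36, 48, 72 and 96; a TCV assessment at discontinuation; events counted at their own date.
- Assumed: exponential PFS with median 150 weeks, S(t) = 2^(−t/150), so S(95) = 0.645, S(97) = 0.639 and S(144) = 0.514. Discontinuation is independent of PFS: none, or exponential with median 104 or 52 weeks. Each TCV assessment is clean and post-study treatment follows at once, so later events do not count.
- Follow-up of 199–290 weeks for 34 subjects: 10 April 2019 to 31 January 2023 is 1,392 days, and 1,392/7 = 198.9 weeks. The SAP date is an assumed cutoff and the upper end is assumed.
- Follow-up of 120–200 weeks for 80 subjects: wholly assumed.

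**Step 3: Week 144 PFS under the SAP rule (true 0.514).**

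| Discontinuation | 199–290 weeks | 120–200 weeks |
|---|---|---|
| Median 52 weeks | 0.50 | 0.42 |
| Median 104 weeks | 0.48 | 0.34 |
| None (extreme case) | 0.38 | 0.17 |

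With discontinuation, the reported medians are 140–148 and 120–129 weeks against a true 150. If a quarter of the 12-weekly visits after Week 96 carry a clean IWG assessment, Week 144 PFS is 0.51–0.52 and 0.45–0.47.

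**Step 4: before Week 96.** With both follow-up ranges above, Week 95 PFS is 0.64–0.65 against 0.645, so there is almost no bias. That depends on follow-up. SAP 11.0 ties each cohort's analysis to Week 24, and Protocol Amendment 11 (synopsis dated 4 October 2021) calls only Cohort 1a fully enrolled. If Cohort 1b was still open then, its shortest follow-up to 31 January 2023 is at most 484/7 = 69 weeks. Shorter ranges, across the three discontinuation scenarios, give:

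| Follow-up | Week 95 (true 0.645) | Week 97 (true 0.639) |
|---|---|---|
| 69–180 weeks | 0.632–0.635 | 0.614–0.626 |
| 24–120 weeks | 0.592–0.597 | 0.537–0.582 |

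Here the cause is data cutoff between scheduled assessments: an event in the gap counts, while an event-free subject goes back to the previous assessment. With 24–120 weeks, a true median of 72 weeks reads 65–66.

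**The case against.** **The size is assumed.** This stands. The 150-week median has no source in the documents. Events include relapse, such as loss of anemia or spleen response for a month or more, so the true median may fall well before Week 96. Protocol 5.6 says about half of patients stop ruxolitinib within 2–3 years, so the no-discontinuation figures (0.38 and 0.17) are an extreme and not an expected size. Late clean assessments are permitted, and they shrink the bias. Cohorts 2 and 3 were not simulated.

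**PFS is exploratory, with no formal test.** This also stands and limits the consequence to a reported estimate.

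**The wider rule for duration of SVR35 does not make the PFS rule wrong.** Agreed: it shows only that other censoring sources are already in use. The error lies in the PFS rule combined with the schedule.

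**Truncation discards observed events.** True, and it is the price of the fix.

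**Stronger readings that the documents do not support.** A reader might infer that the protocol and SAP conflict on ruxolitinib continued after navitoclax. Protocol 5.1 moves a subject to survival follow-up when "the subject begins a post-study treatment for MF other than the continuation of ruxolitinib (Cohorts 1a, 1b or 3"), whereas SAP 6.4 says "Ruxolitinib administered after the last dose of navitoclax for Cohort 1 (Cohorts 1a and 1b) is considered as post-study treatment". The first governs visits and the second classifies treatment for analysis, consistently with SAP 8.1, so this is not a conflict. A reader might also infer bias after treatment ends. None is claimed: in Cohorts 1a and 1b, events after post-study ruxolitinib starts do not count.

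**Conclusion.** The point holds. SAP 8.5.1.9, read with the protocol's assessment schedule, makes censoring after Week 96 depend on outcome. The later PFS curve, and any median falling there, is biased downward unless clean assessments continue. The direction follows from the text; the size does not. Under the stated assumptions, Week 144 PFS is low by about 0.01 to 0.04 with long follow-up and by 0.10 to 0.17 with 120–200 weeks, when subjects discontinue.

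It would be tempting to add that everything before Week 96 is safe. That is so only if almost all subjects have at least 96 weeks of potential follow-up. Otherwise cutoff between assessments lowers the curve by about 0.01–0.02 (69–180 weeks) or 0.05–0.10 (24–120 weeks) at Weeks 95–97. Nor does the point reach beyond PFS: no primary endpoint, secondary endpoint, OS result or decision rule is affected. The change is worth making because a planned estimate can be materially wrong and the correction is cheap.

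**What to change.** In SAP 8.5.1.9:

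1. Present the main PFS curve, median and any landmark only to Week 96 (the scheduled assessment with its 7-day window). Administratively censor subjects still at risk there and list later events. Report the median as not reached if the curve is still above 50%.
2. Show numbers at risk. For any analysis in which subjects have less than 96 weeks of potential follow-up, state that truncation does not remove the bias from cutoff between assessments.
3. Add one sensitivity analysis that censors event-free on-treatment subjects at their last on-treatment clinic visit with spleen palpation (12-weekly after Week 24, Protocol Synopsis). Label it optimistic if progressions go undocumented. In the two longer follow-up ranges this gives Week 144 PFS of 0.51–0.52 against 0.514.

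Separately, reconcile two protocol statements on follow-up after treatment. Section 5.1 says "a Post-Treatment Follow-up visit will be performed approximately 12 weeks following TCV, then every 12 weeks thereafter to assess disease" status, while the Table 6 footnote has disease assessment at those visits only if progression is suspected. Until that is settled, do not take a post-treatment visit as a progression-free date unless disease status was recorded there.

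The cost is SAP wording and one extra output from data already collected. The downside is that progressions and deaths after about Week 96 leave the main PFS estimate and are listed only.
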